9.2.2. Exclusion Criteria

Patients meeting the following criteria will not be included in the study:

1. Currently on both Rimegepant and triptan use at time of survey.

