9.3. Variables

The NHWS includes self-reported data on demographics, health characteristics, disease history, and health outcomes. The Table 1 below provides further details on the specific variables that will be assessed in the study.

Table 1. Study Variables

Variable	Role	Operational Definition
Rimegepant vs. triptan use	Exposure	Current Rimegepant users (for sensitivity analysis restricted to acute Rimegepant users with <12 days use per month) vs. triptan users (no OTC, oral route only).
Outcomes: Migraine treatment use and treatment satisfaction		
Migraine medication type (drug or OTC)	Outcome	Defined as drug only, OTC only and both drug and OTC, based on current use of migraine medication classes
Migraine treatment type (acute or prevention)	Outcome	Defined as acute only, prevention only and both acute and prevention, based on current use of migraine medication classes
Total number of acute migraine agent drug (continuous)	Outcome	Total number of acute agent classes (both drug and OTC) used
Total number of acute migraine agent drug (categorical)	Outcome	Including 1 drug class, 2 or more drug classes, and 3 or more drug classes based on the total number of acute agent (both drug and OTC) classes used
Total number of prevention migraine agent drug (continuous)	Outcome	Total number of prevention agent classes (only drug) used
Total number of prevention migraine agent drug (categorical)	Outcome	Including 1 drug class, 2 or more drug classes, and 3 or more drug classes based on the total number prevention agent classes (only drug) used
Current migraine treatments (drugs)	Outcome	Defined as yes or no for current migraine treatments on drug classes including: Rimegepant, triptans, NSAIDs, opioids, barbiturates, ergots, gepants (acute, including Rimegepant), ditans, combination analgesics, other acute drugs, anticonvulsants, beta-blocker, antidepressant, CGRP mAb, botox, and gepant (prevention, including Rimegepant)
Treatment satisfaction (drugs)	Outcome	Treatment satisfaction of drug classes of: Rimegepant, all acute agents, triptans, NSAIDs, opioids, barbiturates, ergots, gepants (acute), ditans, combination analgesics, other acute treatment, all prevention agents,

		anticonvulsants, beta-blockers, antidepressants, CGRPs mAb, botox, and gepant (prevention) Categorized into 7 categories: extremely dissatisfied, very dissatisfied, somewhat dissatisfied, neither dissatisfied nor satisfied, somewhat satisfied, very satisfied, extremely satisfied

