9.5. Study Size

Sample size estimates, based upon preliminary feasibility, are provided below, in Table 2. The sample size for this study is fixed by the number of patients in the NHWS database who meet the imposed criteria.

Table 2. Estimated Sample Sizes

Patient Cohorts	n
Overall NHWS sample	75,007
Diagnosed with migraine	8,439
Triptan users (oral route only, no OTC) without Rimegepant use	1,340
Rimegepant users without triptan use	144
Rimegepant users (acute only) without triptan use*	112

*For sensitivity analysis.

Abbreviations: NHWS: National Health and Wellness Survey; OTC: over the counter

A sample size of 1) 130 and 2) 100 in each group (1:1 allocation) will have 80% power to detect an effect size of at least 1) 0.35 standard deviation (SD) units (indicative of at least a “small-to-medium” effect) and 2) 0.4 SD units (indicative of a medium effect), respectively, using a 2-group t-test with a 5% 2-sided significance level. We will have a sample size much greater than 130 in one of our groups, resulting in higher statistical power compared to the 1:1 allocation mentioned above. A total sample size of 100 will have 80% power to detect an effect size from a chi-square distribution of at least 0.33 (indicative of at least a “small-to-medium” effect) using a chi-square test with a 5% 2-sided significance level and 3 degrees of freedom. There will be sufficient power to detect a “small-to-medium” effect of Rimegepant user vs. triptan use on the outcomes in the main analysis, and sufficient power to detect a medium effect in the sensitivity analysis with acute Rimegepant users only.

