9.7. Data Analysis

The average treatment effect of treated (ATT) will be measured to evaluate the effects of Rimegepant vs. triptan among current Rimegepant users.

Based on clinical relevance, we will prespecify a list of variables to adjust for the comparison.

Inverse probability of treatment weighting (IPTW) will be conducted to adjust for confounding by the covariates. The propensity score for each participant will be estimated by logistic regression and by including the prespecified list of variables to adjust for. Weights for ATT will be calculated for both exposed (Rimegepant users) and unexposed group (triptan users)¹⁶. Stabilized weights will be used to address extreme weight values.

To confirm that the IPTW procedure is successful, the weighted Rimegepant users and triptan users will be compared on the covariates using standardized mean difference (SMD) to ensure both groups are adequately balanced across all weighting criteria. While there is no definitive cut-off for identifying imbalance in IPTW, as a rule of thumb, a standardized mean difference (SMD) that is >0.10 is indicative of imbalance¹⁷. This threshold will be applied to determine the quality of the weighting.

Once the weighting is confirmed to be successful, bivariate analyses will be conducted to compare the weighted cohorts on treatment satisfaction, HCRU, QoL, migraine-specific

disability, and work productivity loss. Specifically, categorical variables will be analyzed using chi-square tests or Fisher's exact tests for small samples; continuous variables will be analyzed using 2-sample t-tests. Non-parametric tests may be considered for comparisons on skewed variables (e.g., HCRU) when the sample size is small (e.g., <30). For bivariate comparisons, p-values <0.05, 2-tailed, will be considered statistically significant. If there are covariates that are unbalanced after weighting (i.e., SMD >0.1), those covariates will be adjusted for in the regression analysis of outcomes. Generalized linear models will be fit depending on the distributions of outcomes.

As a sensitivity analysis, the aforementioned IPTW and bivariate comparisons will be replicated after restricting the Rimegepant user cohort to the subset of those presumed to be acute treatment users (<12 days using Rimegepant).

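### Treatment satisfaction is a 7-level ordered rating with no ordinal method assigned to it; naming one, and naming the index-drug comparison, is a cheap improvement

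*Combined protocol and SAP*

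**What the plan says.** Section 8 lists treatment satisfaction first among the outcome domains of the primary aim. Table 1 in section 9.3 has one drug-satisfaction entry, defined as "Treatment satisfaction of drug classes of: Rimegepant, all acute agents, triptans, NSAIDs, opioids, barbiturates, ergots, gepants (acute), ditans, combination analgesics" and further classes. That makes 18 items, including the pools of all acute and all prevention agents. The response scale is given as "Categorized into 7 categories: extremely dissatisfied, very dissatisfied, somewhat dissatisfied" and so on up to extremely satisfied. A second entry rates four OTC classes on the same scale.

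The exposure entry contrasts current Rimegepant users with "triptan users (no OTC, oral route only"). Section 9.2.2 excludes patients "Currently on both Rimegepant and triptan use at time of survey".

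In section 9.7, "bivariate analyses will be conducted to compare the weighted cohorts on treatment satisfaction" and the other domains, and "categorical variables will be analyzed using chi-square tests", or Fisher's exact tests for small samples. Two other sentences there might reach satisfaction:
- "Non-parametric tests may be considered for comparisons on skewed variables (e.g., HCRU) when the sample size is small", with fewer than 30 as the example.
- Generalized linear models are to be fitted according to the outcome distribution. This follows the provision for covariates left unbalanced after weighting, and no ordinal model is named.

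**The concern.** A chi-square or Fisher test on a 2 x 7 table treats the seven levels as unordered labels. It asks whether the two distributions differ in any way, and it returns a p-value without a sign or an effect size. If one cohort is simply more satisfied, most of that test's degrees of freedom are spent on patterns nobody expects. The non-parametric sentence is optional and limited to skewed variables in small samples, whereas the cohorts here are 144 and 1,340. The model sentence does not pick an ordinal model.

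A smaller gap sits beside this. No sentence says which rating, or which pair of ratings, is the between-cohort satisfaction result. A class or pooled item could be reported as that result, and no scoring rule is given for a patient who uses several agents in a pool. Section 8 says findings may inform payer communications, so the choice is better made before analysis.

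**Working it through.** **Inputs from the documents.** Seven ordered levels (9.3, Table 1). Cohorts of 144 Rimegepant users, 112 acute-only Rimegepant users and 1,340 triptan users (9.5, Table 2). Two-sided alpha 0.05 (9.7). Effect sizes 0.35 and 0.40 SD (9.5), which the plan states for a t-test and does not set for satisfaction.

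**Assumptions.** The documents give no satisfaction distribution. Three were assumed for the triptan cohort, lowest to highest level:
- A (.03, .05, .09, .13, .28, .27, .15)
- B (.05, .10, .18, .34, .18, .10, .05)
- C (.02, .03, .05, .08, .20, .32, .30), which is ceiling-heavy

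**Step 1: the plan's own figures.** Section 9.5 says 130 per group "will have 80% power to detect an effect size of at least 1) 0.35 standard deviation (SD) units", and 100 per group for 0.40 SD. The noncentrality of the t-test is d x sqrt(n/2): 0.35 x sqrt(65) = 2.82 and 0.40 x sqrt(50) = 2.83. Power is 80.3% and 80.4%. Both reproduce.

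**Step 2: why order matters.** A 2 x 7 table has (2-1) x (7-1) = 6 df; a rank or proportional-odds test uses 1 df. For 80% power at alpha 0.05 they need noncentrality 13.62 and 7.85, a ratio of 13.62/7.85 = 1.74. Under a proportional shift the two tests carry nearly the same signal. For example, at an odds ratio of 1.6 with 144 versus 1,340 and a skewed baseline, the noncentralities are 9.02 and 8.85. The extra degrees of freedom are therefore mostly cost.

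**Step 3: power under a shift.** Cut-points are c_k = Phi^-1(cumulative probability). The shifted cohort has level probabilities Phi(c_k - d) - Phi(c_(k-1) - d), with d in either direction, so three distributions give six scenarios. Pearson chi-square is compared with the tie-corrected Wilcoxon test by unweighted simulation.

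| Comparison | Difference | Chi-square | Rank test |
|---|---|---|---|
| 144 vs 1,340 | shift 0.35 SD | 74-87% | 96-97% |
| 112 vs 1,340 | shift 0.40 SD | 74-88% | 96-97% |
| 144 vs 1,340 | shift 0.25 SD | 38-57% | 76-78% |
| 144 vs 1,340 | spread x 1.3, no shift | 74-85% | about 7-9% |
| 112 vs 1,340 | spread x 1.3, no shift | 64-77% | about 7-9% |

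With no difference, both tests reject about 5% of the time. Repeat runs move the limits by a point or two (down to 74% for the rank test at 0.25 SD). At 0.35 and at 0.40 SD, chi-square power is about 80% or more in five of the six scenarios. The 74% comes from one scenario, distribution C shifted further upward. The 0.25 SD row is close to the smallest shift a t-test would detect with 80% power at these cohort sizes: (1.96 + 0.84) x sqrt(1/144 + 1/1,340) = 0.25 SD.

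**Step 4: a second shift model.** Under proportional odds with three other assumed baselines, 0.35 SD corresponds to an odds ratio of exp(0.35 x pi/sqrt(3)) = 1.89. For 144 versus 1,340, analytic power is 88-90% for chi-square and about 98% for the ordinal test. The odds ratio detectable with 80% power is 1.76-1.78 for chi-square and 1.54-1.56 for the ordinal test. The ordering is the same and the gap smaller. The analytic chi-square figure is slightly optimistic: at an odds ratio of 1.6 and a skewed baseline, simulation gave 53% where the formula gave 59%.

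**Step 5: who rates what.** Current users of both drugs are excluded. No single drug item therefore contrasts Rimegepant with the oral triptan, unless patients also rate drugs they are not currently taking, which the documents do not settle. The pooled items mix in other drugs, and the triptan satisfaction item is not itself limited to the oral route. The main Rimegepant cohort takes any current user. Of its 144, 112 are in the acute-only subset and 144 - 112 = 32 are not.

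**The case against.** The strongest reply is that chi-square on a 2 x 7 table is valid and holds its type I error, so the choice is one of preference. That stands as to validity. It also stands that the ordinal test wins only for a shift. If satisfaction is polarised, the plan's test is far better, and the documents do not say which pattern is expected. At the plan's own effect sizes chi-square mostly reaches 80%. What remains is the loss for smaller shifts and the absence of an effect estimate for a primary-aim outcome.

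Three stronger readings are tempting and are not supported:
- A reader might infer that the 3-df chi-square power statement in section 9.5 is wrong because satisfaction has seven levels. The section does not tie that statement to satisfaction, a 2 x 4 table exists in the plan (MIDAS grade I-IV), and the figure reproduces at 79.9%.
- A reader might infer that the Rimegepant-triptan satisfaction comparison is impossible because each drug is rated in one cohort only. That rests on an assumed survey filter. Setting each cohort's rating of its own drug against the other is the natural reading of Table 1 with section 9.7, so what is needed is mostly a clarification.
- A reader might infer that the direction of any difference would be invisible. The weighted category proportions would show it; what is missing is one summary estimate with an interval.

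**Conclusion.** The point holds as a cheap improvement. The plan assigns an ordered primary-aim outcome to tests that ignore order, and no other sentence in section 9.7 supplies an ordinal method. For a shift along the scale with 144 versus 1,340 patients, an ordinal test raises power from 74-87% to 96-97% at 0.35 SD, and from 38-57% to 76-78% at 0.25 SD. These sizes rest on assumed distributions, a latent-normal shift and unweighted data. The actual analysis is ATT-weighted, and its effective sample size is unknown. The gain reverses for a pure spread difference. Nothing here shows an invalid test, a wrong power figure or an inadequate study size. The unnamed comparison is a matter of clarification.

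**What to change.** In section 9.7, assign satisfaction to one prespecified ATT-weighted ordinal method: either a proportional-odds model or a weighted rank-based test, with robust standard errors. Report an effect estimate with 95% CI and place the weighted 7-level distribution beside it.

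In Table 1, name the between-cohort comparison as each cohort's rating of its own index drug (Rimegepant rating versus oral-triptan rating), and label the other class and pooled ratings as descriptive. State that in the main analysis the Rimegepant rating mixes acute and preventive users. Repeat the same comparison with the same method in the acute-only sensitivity analysis.

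The cost is one derived variable and one model line, with no new data. A proportional-odds model adds an assumption to check; a rank-based test does not. Either has little power against a pure spread difference (about 7-9%, against 64-85% for chi-square at a 1.3-fold spread), which is why the weighted 7-level table should be reported as well.

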Current migraine treatments (OTC)	Outcome	Defined as yes or no for current migraine treatments on OTC classes of analgesics (acetaminophen only), analgesics (combinations), NSAIDs, other OTCs
Treatment satisfaction-analgesics (acetaminophen only)	Outcome	Treatment satisfaction of OTC classes of analgesics (acetaminophen only), analgesics (combinations), NSAIDs, and other OTCs Categorized into 7 categories: extremely dissatisfied, very dissatisfied, somewhat dissatisfied, neither dissatisfied nor satisfied, somewhat satisfied, very satisfied, extremely satisfied
Outcomes: HRQoL		
RAND-36	Outcome	PCS, MCS, and GCS index scores of the RAND-36 ¹²
EQ-5D-5L	Outcome	Health state utilities and the EuroQoL Visual Analog Scale (EQ-VAS) ¹³
WPAI-GH	Outcome	Absenteeism (% of work time missed because of one's health in the past 7 days), presenteeism (% impairment experienced while at work in the past 7 days because of one's health), overall work impairment (combination of absenteeism and presenteeism), and activity impairment (% impairment in daily activities because of one's health in the past 7 days) among total population, employed, unemployed, and disabled ¹⁴
MIDAS	Outcome	Total score, categorical (grade I-IV), and item scores (1-7) of MIDAS ¹⁵
Outcomes: HCRU		
ER visits	Outcome	Visited ER in past 6 months (yes or no); number of ER visits in past 6 months among total population and participants with ER visits
Hospitalizations	Outcome	Was hospitalized in past 6 months (yes or no); number of hospitalizations in past 6 months among total population and participants with hospitalizations
General practitioner/family practitioner visits	Outcome	Visited general practitioner/family practitioner in past 6 months (yes or no); number of general practitioner/family practitioner visits in past 6 months among total population and participants with general practitioner/family practitioner visits
Cardiologist visits	Outcome	Visited cardiologist in past 6 months (yes or no); number of cardiologist visits in past 6 months among total population and participants with cardiologist visits
Neurologist visits	Outcome	Visited neurologist in past 6 months (yes or no); number of neurologist visits in past 6 months among total population and participants with neurologist visits

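### Section 9.7 defines its balance check for the whole weighted cohorts, but Table 1 also compares visit counts among visitors (conditioning on an outcome) and WPAI-GH within employment subsets (balance unchecked)

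*Combined protocol and SAP*

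**What the plan says.** Section 9.7 names the estimand: "The average treatment effect of treated (ATT) will be measured to evaluate the effects of Rimegepant vs. triptan among current Rimegepant users". One model supplies the weights: "The propensity score for each participant will be estimated by logistic regression and by including the prespecified list of variables to adjust for". The two weighted groups are then compared by SMD "to ensure both groups are adequately balanced across all weighting criteria", with 0.10 as the threshold. Testing comes next: "Once the weighting is confirmed to be successful, bivariate analyses will be conducted to compare the weighted cohorts on treatment satisfaction, HCRU, QoL, migraine-specific"; the list goes on to disability and work productivity loss. Residual imbalance has its own remedy: "If there are covariates that are unbalanced after weighting (i.e., SMD >0.1), those covariates will be adjusted for in the regression analysis of outcomes".

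Table 1 (section 9.3) sets the populations for each outcome. ER use is recorded as any visit, yes or no, and as "number of ER visits in past 6 months among total population and participants with ER visits". Hospitalizations and general practitioner, cardiologist, neurologist and traditional provider visits follow the same pattern, so there are six visitor-only counts. WPAI-GH is planned "among total population, employed, unemployed, and disabled". Employment enters the weighting list as a yes/no covariate.

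The plan does not provide for re-estimating weights, re-checking SMDs or naming an estimand inside any of these subsets. The weighting is repeated only for the acute-user cohort and with NHWS sampling weights. Section 9.9 does not list the matter as a limitation.

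**The concern.** ATT weights make the triptan cohort resemble the Rimegepant cohort as a whole. Once the comparison is confined to part of each cohort, that resemblance is no longer guaranteed. The two kinds of subset raise different problems.

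- **Visitors only.** Having a visit is one of the outcomes. If treatment changes who visits, the visitors in the two arms are different kinds of patient, and a difference in their counts is not an effect of treatment among current Rimegepant users. Adjustment within visitors can deal with measured covariates. It cannot deal with unmeasured ones, and it does not restore the stated estimand.
- **Employment subsets.** Absenteeism and impairment while working have meaning only for people who work, so restricting to them is proper. Work productivity loss, one of five outcome domains, then rests on a group in which the plan's own balance criterion is never applied.

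Section 8 says that the findings may be used with payers, so a significant row in either set could be quoted as if it had passed the balance check.

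**Working it through.** **1. The plan's own figures.** Section 9.5 gives power for whole groups only. Two-sample t-test power is 80.3% for 130 per group at 0.35 SD and 80.4% for 100 per group at 0.4 SD. Chi-square power with N=100, effect size 0.33 and 3 df is 79.9% (noncentrality 100 × 0.33² = 10.89). These reproduce and are not in dispute. No figure is given for a subset.

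**2. Are the visitor-only rows meant to be tested?** Section 9.7 puts HCRU through tests at p<0.05 and allows non-parametric tests for skewed variables such as HCRU when samples are below about 30. The cohorts in Table 2 are 144 (112 in the acute-user analysis) and 1,340, so samples that small would most plausibly arise among visitors. This is an inference; the plan does not say so outright.

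**3. Size of the visitor-only bias (assumed inputs).** One million respondents; one standard normal covariate x; exposure logit −2.4 + 0.5x; visit logit −1.8 + 1.0x + log(OR) for Rimegepant; count given a visit 1 + Poisson(exp(−0.3 + 0.4x)), with no treatment term. Weights are 1 for Rimegepant and e/(1−e) for triptan. Full-cohort SMD is about 0 throughout.

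| OR for any visit | SMD among visitors | Mean count, visitors (Rimegepant vs triptan) | Mean count, total population |
|---|---|---|---|
| 1 | −0.01 | 2.21 vs 2.22 | 0.54 vs 0.54 |
| 0.8 | 0.04 | 2.24 vs 2.22 | 0.47 vs 0.54 |
| 0.6 | 0.08 | 2.26 vs 2.22 | 0.38 vs 0.54 |
| 0.5 | 0.11 | 2.26 vs 2.22 | 0.34 vs 0.54 |

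The first row shows simulation noise of about 0.01. In the last row the visit rates are 15.1% vs 24.3%, and 0.151 × 2.26 = 0.34 against 0.243 × 2.22 = 0.54. The total-population count shows the reduction, while the visitor-only count leans slightly the other way. With a covariate coefficient of 0.5 instead of 1.0, the last-row SMD falls to about 0.055 and the counts to 2.117 vs 2.114.

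**4. What that bias does to a test.** At those rates the cohorts yield about 144 × 0.151 = 22 and 1,340 × 0.243 = 326 visitors. If the SD of the count is 1 to 2 visits (assumed), SE = SD × √(1/22 + 1/326) = 0.22 to 0.44. A bias of 0.04 is then about 0.1 to 0.2 SE, and two-sided type I error moves from 5% to between about 5.1% and 5.5% (normal approximation, weight variance ignored).

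**5. Employment subsets (assumed inputs).** One million respondents, 60% employed, propensity model with main effects for x and employment only.

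| Omitted x-by-employment interaction | SMD, all | SMD, employed | SMD, not employed |
|---|---|---|---|
| 0 | 0.00 | 0.00 | 0.01 |
| 0.3 | 0.00 | 0.11 | −0.19 |
| 0.6 | 0.01 | 0.21 | −0.38 |

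The whole-cohort check passes in all three rows. The binary covariate also does not separate unemployed from disabled respondents, so the model carries no term for that distinction.

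**6. Chance imbalance, kept apart from bias.** With exact full-cohort balance and random membership of a fraction f, SE(SMD) = √[(1−f)(1/(144f) + 1/(1340f))]. At f = 0.6 this is √[0.4 × (1/86.4 + 1/804)] = 0.072, so P(|SMD|>0.1) = 16%. A weighted simulation with 20 covariates and a correct propensity model (200 datasets) agrees: 0% of covariates exceed 0.1 in the full cohort and about 15% in a 60% employed subset, or about 3 of 20. Among assumed visitors of 13 to 15% the share is about 64%. Treatment did not affect visiting in that simulation, so none of this is selection bias.

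**7. Precision.** The detectable difference at 80% power is about 2.80 × √(1/144 + 1/1340) = 0.25 SD in the full cohorts. It is 0.78, 0.55 and 0.32 SD if 10%, 20% or 60% of each cohort is in the subset (assumed fractions, weight variance ignored).

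**The case against.** The best defence is that the main HCRU results are untouched. Every row already includes any visit and the total-population count, both consistent with the ATT, so the visitor-only count is a third, supplementary view. Its bias is small under a strong assumed effect and vanishes without one. Section 9.9 also disclaims causal inference. For WPAI-GH, employment is in the propensity model, so full-cohort weights balance the employed in expectation if that model is adequate, and the imbalances in step 5 come from interactions that were assumed. All of this stands and limits the point. It does not supply an estimand for the visitor-only p-values or a check for the subsets.

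Several stronger readings are tempting and are not supported:

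- That a visit is a post-exposure event. Section 9.2.1 defines exposure as current use at the survey, and visits look back 6 months. No treatment start date is given, so some visits may precede treatment.
- That selecting visitors undoes the weighting. The visitor SMD stays below 0.1 for odds ratios of 0.8 and 0.6, and near zero for 1.
- That the high chance of subset SMDs above 0.1 (16% per covariate at f = 0.6, and 70% at f = 0.1 by the same formula) shows bias. It measures sampling variation under assumed fractions, has zero expected bias, and would appear in subsets of a randomised trial.
- That the plan rules out subset checks. It is silent.

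**Conclusion.** The point holds in a limited form. The six visitor-only comparisons condition on an outcome and do not estimate the ATT in section 9.7. Their bias depends on treatment affecting visiting; in the example it is about 0.04 visits when the odds are halved, small against the sampling error of about 22 Rimegepant visitors. The WPAI-GH subset results can stand as an ATT within each subset if the propensity model is adequate there, and the planned whole-cohort check cannot show whether it is: it reads near 0 while SMDs of 0.11 to 0.21 exist in the employed under the assumed interactions. The subset fractions, effect sizes and interactions are all assumptions, because the documents give none. The any-visit and total-population HCRU analyses are not affected.

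**What to change.** 1. In section 9.7 and Table 1, state that the six counts among participants with visits are descriptive and carry no p-values, and that HCRU inference rests on the any-visit and total-population comparisons already planned.
2. Repeat the SMD table within each WPAI-GH subset that is compared (employed, unemployed, disabled), apply the existing >0.1 regression rule there, and label each result as an ATT within that subset.

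The cost is six fewer tested rows and one balance table per subset. The adjusted models will also carry more covariates, about 3 of 20 in a 60% employed subset by chance alone and more in smaller subsets, where there are fewer respondents to support them. No new data are needed.
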